#### 5.1 Planned Duration of Protocol

Stage 1 will take up to six months (full dose group) or four months (medium and low dose groups) to complete after screening and baseline evaluation. The screening and baseline evaluation can take up to 4 months. In addition, if the length of time between the end of tapering and the first experimental session is longer than a month, the CAPS should be repeated to show consistency between this score and the baseline CAPS. The open-label study segment for participants initially assigned to receive low dose or medium-dose MDMA (Stage 2) will last an additional five months from the single introductory and review psychotherapy session until the evaluation two months after the final open-label MDMA-assisted psychotherapy session. The time period between the end of Stage 1 and the start of Stage 2 should not exceed 5 months for any participant with CAPS re-assessment done if there is an interval of greater than 8 weeks between the end of Stage 1 and the beginning of Stage 2. The 12-month follow-up will occur a year after the final experimental session for all participants who complete Stage 1 only, and a year after the final open-label session for any participants who enroll in and complete

Stage 2. For each participant who enrolls only in Stage 1, the entire study duration will be up to 1.5 years including the 12-month long-term follow-up, and for the participants that complete both Stage 1 and Stage 2 follow-ups, the study may take about two years.

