A =First Integrative session is 1 day after exp session B = At least 24 hrs prior to 1st exp. session C =Approximately 6 hours post MDMA D =At the beginning of the session E =As needed F=Approximately every 60 minutes G =Given on 2nd preparatory session after meds are tapered (V3) H = Only for subjects starting Long term Follow up and not going to Stage 2 I =For 7 days post Exp. Session, C-SSRS D2 and D7 of calls only, General well being for all 7 days J =Subjects in the medium or low dose group will not have visits 14-18, but will instead move onto Stage 2. K= On the day of the 1st integrative session following the Exp. Session I =CAPS may be videotaned M=First preparatory session (V2) may happen at the time of screening, before enrollment. N= Full dose subjects only. O= Only in subjects with pre-existing timitus and/or chronic pain

Table4.Stage2Time&Events	Preparatory	Experiment	tal Session 1	on 1 Experimental Session 2			Experimen	tal Session 3	Follow-Up		Long Term Follow-Up
Visit #	V19*	V20	V 21,22,23	V24	V 25,26,27	V28	V29	V 30,31,32	V33		1 Year Follow-up
Type of Visit	Preparatory Session	Experimental Session 1	Integrative Sessions	Experimenta 1 Session 2	Integrative Sessions	Secondary endpoint	Experiment al Session 3	Integrative Sessions	End of Stage 2 & Outcome		Follow-Up & Outcome
Visit Timing or Study day or Window	Within maximum of 5 months of V13*	After V19	Before V24 A	3-5 weeks post V20	Before V28 A	1 month post V24, beforeV29	3-5 weeks post V24	Before V33	May happen over > 1 day 2 months post V29		May happen over > 1 day. One Year post V14 or V29
Confirm Informed Consent	X										
Confirm Inclusion/Exclusion	X										
Enrollment in Stage 2	X										
Collect Concomitant Medication	X	X	X	X	X	X	X	X	X	7	X
Record to Audio/Video	X	X	X	X	X	$X^{H}$	X	X	$X^{H}$	Stage	
General Well-Being	X	X	X	X	X		X	X	X	Sta	
Drug Screen		X		X			X			or ,	
Pregnancy Screen (if applicable)		X		X			X			_	
CAPS, GAF, BDI-II, PTGI, PSQI, DES-II (IR)	Use V13*					X			X	Stage	X
NEO PI with Ind. Rater	Use V13*								X	er	X
C-SSRS	X	X C, D, E	$X^{G}$	X C, D, E	X G		X C, D, E	X G	X	after	X
Administer IP Drug + Therapy, SOCQ		X		X			X			dn	
Monitoring of BP, Pulse and Temp.		X		X			X			Follow	
SUD		X D, F		X D, F			X D, F			o	
Overnight Stay		X		X			X				
Integrative Therapy Session			X		X			X		Term	
7 days Integrative Telephone Contact			X G		X G			X G		Ī,	

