## 6.2.7 Evaluation at Primary Endpoint & Unblinding (Visit 13)

The primary endpoint evaluation in Stage 1 will occur one month after the second blinded experimental session. This visit will consist of two meetings that may be completed on separate days, one with the independent rater and the other with the therapists. The blinded independent rater will administer: CAPS to assess PTSD symptoms, BDI-II to assess depression symptoms, GAF to assess general psychological function, PTGI to assess post-traumatic growth (in reference to start of the study), PSQI to assess sleep quality, DES-II to assess dissociation symptoms and NEO PI to assess personality. The blinded independent rater will provide their belief of the subject's condition assignment.

After completing all assessments and measures with the independent rater, the subject will meet with the therapists for approximately 30 minutes. Following the visit with the independent rater the blind will be broken for the subject's condition assignment. The independent rater will remain blind to condition assignment at this time. The therapists will assess suicidality with the C-SSRS. The visual analog scale will be used to collect

changes in subjects who have pre-existing tinnitus and chronic pain symptoms.

If the subject had been assigned to receive medium dose or low dose MDMA, the therapists will discuss continuation to Stage 2. Low and medium dose subjects will not complete the third experimental session and associated integrative sessions in Stage 1. Participants who decline continuing to Stage 2 will complete the Responses to Research Participation Questionnaire (RRPQ). If participants had been assigned to the full dose condition in Stage I, they will provide their perceptions of experimental sessions at this point. The therapists will discuss scheduling the third open label full dose experimental session and integrative sessions.

Adverse Events and medications will be collected as described in Sections 8 and 9 of the protocol.

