# 6.2.8 Evaluation Two Months after the Third Experimental Session (Visit 18-Full dose subjects only, End of Stage 1)

The final evaluation for full dose subjects in Stage 1 will occur two months after the third experimental session. Participants will meet the independent rater for 90 to 120 minutes. The independent rater will administer the CAPS, BDI-II, PTGI (in reference to the start of the study), DES-II and the PSQI. The independent rater will assess participants on the GAF. Administration of CAPS may be recorded to video.

After completing all assessments and measures at the evaluation at the end of Stage 1 with the independent rater, the full dose subjects will meet with the investigators for approximately one hour. The investigators will administer the C-SSRS, and the subjects will indicate their perceptions of a third experimental session. Subjects will complete the RRPQ. The visual analog scale will be used to collect changes in pre-existing tinnitus and chronic pain symptoms.

Subjects will receive a memory aid card for use between this visit and the 12-month follow up. Subjects will use this card to record AEs, medications and changes in psychiatric status that they will be asked about at the termination visit. Memory aids will not be collected. Subjects may return to taking psychiatric medications from this point onward if necessary.

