When each subject completes the evaluation at the primary endpoint, the blind will be broken for that subject. Subjects who had been assigned to receive low dose or medium dose MDMA will subsequently have the opportunity to enroll in the open-label study arm, or “Stage 2.” Stage 2 must start within a maximum of 5 months after the subject finishes Stage 1. The open-label study arm will follow a similar sequence of events and procedures, except that there will be a single preparatory session, and all three MDMA-assisted psychotherapy sessions will be open-label. Subjects will receive an initial dose of 100 mg MDMA in the first experimental session, and one of two active doses of MDMA that are clinically titrated by the CI during the second and third open-label experimental sessions that will otherwise follow the same sequence of events (See Time and Events Table). Outcome measures except for the NEO PI will be repeated one month after the second Stage 2 experimental session, and all outcome measures will be repeated at the end of Stage 2.

The study will conclude with a one-year follow-up occurring 12 months after the final experimental session of Stage 1 for subjects who received full dose MDMA or who elected not to enroll in Stage 2 after receiving either the medium or low doses in Stage 1. Subjects who enrolled in Stage 2 will have their final follow-up 12 months after the final open-label experimental session. Outcome measures will be repeated at the 12-month follow-up, as well as a questionnaire concerning self-reported long-term effects of study participation.

Sub-studies in a select group of subjects in this study may be conducted for exploratory purposes. Subjects will complete a separate consent process if they chose to participate in these studies.

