| Visit #                                    | Preparatory Session                | Experimental Session 1 | Integrative Sessions    | Experimental Session 2 | Integrative Sessions    | Secondary endpoint           | Experimental Session 3 | Integrative Sessions    | End of Stage 2 & Outcome                  | 1 Year Follow-up                                  |
| Type of Visit                              | Within maximum of 5 months of V13* | After V19              | Before V24 A | 3-5 weeks post V20     | Before V28 A | 1 month post V24, before V29 | 3-5 weeks post V24     | Before V33 A | May happen over > 1 day 2 months post V29 | Follow-Up & Outcome                               |
| Visit Timing or Study day or Window        |                                    |                        |                         |                        |                         |                              |                        |                         |   | May happen over > 1 day. One Year post V14 or V29 |
| Confirm Informed Consent                   | X                                  |                        |                         |                        |                         |                              |                        |                         |   |   |
| Confirm Inclusion/Exclusion                | X                                  |                        |                         |                        |                         |                              |                        |                         |   |   |
| Enrollment in Stage 2                      | X                                  |                        |                         |                        |                         |                              |                        |                         |   |   |
| Collect Concomitant Medication             | X                                  | X                      | X                       | X                      | X                       | X                            | X                      | X                       | X   | X   |
| Record to Audio/Video                      | X                                  | X                      | X                       | X                      | X                       | X H               | X                      | X                       | X H                            |   |

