#### Long-term Follow-up

For the CAPS, PTGI, BDI-II, GAF, PSQI, DES-II, and NEO PI, the absolute changes in the measures from baseline to the long-term follow-up visit (one year post final experimental year) will be compared with t-tests. The absolute changes in the measures from long-term follow-up to End of Stage 1 (visit 18, 125 mg) or long-term follow-up compared to End of Stage 2 (visit 33, 30 and 75 mg) will be compared with within-subject t-tests.

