### Columbia Suicide Severity Rating Scale (C-SSRS)

Suicidal ideation and behavior will be summarized according to suggestions made in the Columbia-Suicide Severity Rating Scale Scoring and Data Analysis Guide [3]. A positive response for suicidal ideation is counted when a subject answers "yes" to any one of the five suicidal ideation questions (Categories 1-5) on the C-SSRS, i.e. a score > 0 for suicidal ideation score. Serious suicidal ideation is a suicidal ideation score of 4 or 5. A positive response for suicidal behavior occurs when a subject answers "yes" to any one of the five suicidal behavior questions (Categories 6-10) on the C-SSRS, i.e. a score > 0 for suicidal behavior score. The number and percent of positive responses of Positive Ideation, Serious Ideation, and Positive Behavior will be tabulated by treatment group and time period. P-values will be calculated using the chi-squared test for overall treatment group differences and Fisher's exact test will be used for pairwise testing. Compare lifetime serious suicidal ideation and positive behavior frequencies to cumulative frequencies anytime during the study until end of stage 1 and stage 2 using chi-squared test for overall treatment group differences and Fisher's exact test for pairwise testing.

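### The cumulative C-SSRS comparison in SAP 8.9.4 has no stated contrast and no common cut-off; if doses are compared, Stage 1 counts three sessions for full dose and two for low and medium dose

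*SAP*

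**What the plan says.** The C-SSRS paragraph of SAP 8.9.4 has two parts. The first tabulates positive ideation, serious ideation and positive behavior by treatment group and time period, with a chi-squared test across groups and Fisher's exact test for pairs. The time periods are not defined. The second compares lifetime serious ideation and positive behavior with "cumulative frequencies anytime during the study until end of stage 1 and stage 2 using chi-squared test for overall treatment group differences", again with Fisher's test for pairs. It does not say which two quantities are contrasted, which population is used, or at which visit each group's count stops.

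End of Stage 1 is not the same visit in every group:

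- **Full dose.** SAP 8.9.2.2 (Long-term Follow-up) describes changes "from long-term follow-up to End of Stage 1 (visit 18, 125 mg"). Protocol 6.2.8 agrees: "The final evaluation for full dose subjects in Stage 1 will occur two months after the third experimental session".
- **Low and medium dose.** Footnote J of the Stage 1 Time and Events table: "Subjects in the medium or low dose group will not have visits 14-18, but will instead move onto Stage 2". Protocol 6.2.7: "Low and medium dose subjects will not complete the third experimental session and associated integrative sessions in Stage 1".
- **Visit 13 as their last Stage 1 visit.** SAP 4.0 states "Stage 2 must start within a maximum of 5 months after the subject finishes Stage 1", and the Stage 2 Time and Events table gives the same limit as "Within maximum of 5 months of V13".
- **Duration.** Protocol 5.1: "Stage 1 will take up to six months (full dose group) or four months (medium and low dose groups) to complete".

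The blind is broken for each subject at visit 13 (SAP 4.0), so everything after it is open-label.

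**The concern.** Comparing suicidality between conditions is a stated safety objective (Protocol 3.3, SAP 3.3). A cumulative proportion depends on how long and how often subjects are observed. If full dose is counted through a third session and two further months while the other groups stop at visit 13, a higher full-dose percentage is expected even when MDMA dose has no effect on suicidality. A reader of the table could take that excess for a dose effect on serious ideation or behavior. The surplus full-dose data are also collected after unblinding, so blinded and open-label observations are mixed in one group only.

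**Working it through.** The plan gives no event rate, power or error figure for this analysis, so there is none to reproduce. The check counts exposure in each window and then asks what equal risk would look like.

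**1. Scheduled C-SSRS contacts after first dose** (Protocol 6.2.3 to 6.2.8 and the Stage 1 Time and Events table, nominal schedule). Each session has 2 in-session administrations, 3 integrative sessions and 2 telephone days. The pre-dose administration at visit 5 is excluded.

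- Session 1: 1 + 3 + 2 = 6
- Session 2: 2 + 3 + 2 = 7
- Visit 13: 1
- Low and medium dose to visit 13: 6 + 7 + 1 = 14
- Full dose adds session 3 (2 + 3 + 2 = 7) and visit 18 (1): 14 + 8 = 22

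Ratio: 22/14 = 1.57. An integrative session that replaces a call would change these counts slightly.

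**2. Time from first dose** (1 month = 4.35 weeks).

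- To visit 13: 3 to 5 weeks + 1 month = 7.3 to 9.3 weeks
- To visit 18: 6 to 10 weeks + 2 months = 14.7 to 18.7 weeks (minimum 16.0 if visit 14 cannot precede visit 13)

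**3. Cumulative percentage with the same risk at every dose.** Let r be the assumed risk per session and k the number of sessions. With independent sessions the cumulative risk is 1 − (1 − r)^k. For r = 0.10: 1 − 0.9² = 19.0% and 1 − 0.9³ = 27.1%. With within-subject correlation ρ a beta-binomial is used, with a = r(1 − ρ)/ρ and b = (1 − r)(1 − ρ)/ρ. Expected excess = 12 × (three-session risk − two-session risk).

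| ρ | r | Full dose, 3 sessions | Low/medium, 2 sessions | Ratio | Expected excess in 12 |
|---|---|---|---|---|---|
| 0 | 0.02 | 5.9% | 4.0% | 1.49 | 0.23 |
| 0 | 0.05 | 14.3% | 9.8% | 1.46 | 0.54 |
| 0 | 0.10 | 27.1% | 19.0% | 1.43 | 0.97 |
| 0.2 | 0.02 | 4.9% | 3.6% | 1.36 | 0.15 |
| 0.2 | 0.05 | 11.8% | 8.8% | 1.35 | 0.36 |
| 0.2 | 0.10 | 22.7% | 17.2% | 1.32 | 0.66 |
| 0.5 | 0.02 | 3.6% | 3.0% | 1.22 | 0.08 |
| 0.5 | 0.05 | 8.9% | 7.4% | 1.21 | 0.19 |
| 0.5 | 0.10 | 17.4% | 14.5% | 1.20 | 0.34 |

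**4. Which side shows more positive subjects** (12 full dose against the other 12, independent sessions). At r = 0.02, full dose has more in 37% of trials and fewer in 22%, with ties in 42%. At r = 0.10 it has more in 59% and fewer in 23.5%. With equal two-session windows the split is even: 26% each way at r = 0.02 and 40% each way at r = 0.10.

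**5. Chi-squared error rate.** All outcomes of three binomials of size 12, 6 and 6 were enumerated, with an uncorrected Pearson test on 2 df and rejection at p ≤ 0.05 (SAP 8.0).

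| r | 3 vs 2 sessions, ρ = 0 | 3 vs 2 sessions, ρ = 0.2 | 2 vs 2 sessions, ρ = 0 |
|---|---|---|---|
| 0.02 | 0.017 | 0.016 | 0.021 |
| 0.05 | 0.033 | 0.033 | 0.046 |
| 0.10 | 0.044 | 0.041 | 0.051 |
| 0.15 | 0.058 | 0.047 | 0.050 |
| 0.20 | 0.076 | 0.057 | 0.051 |

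With unequal windows the rate passes 0.05 at r of about 0.13 (24% cumulative over two sessions), or about 0.17 (28%) at ρ = 0.2.

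**The case against.** **The sentence compares lifetime with on-study, not dose with dose.** Grammatically that is where it starts. A reader might infer from the rest that a biased between-dose test is definitely planned. The SAP does not settle this. The wording about overall group differences and pairwise tests repeats the preceding between-group sentence and makes a dose comparison the natural reading. If lifetime and on-study frequencies are instead compared within each group, no dose contrast exists and the unequal windows do not confound dose. The lack of a stated contrast stands on either reading.

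**The table by time period already serves the objective.** It could, if its periods are cut at visit 13. They are undefined, so neither alignment nor misalignment is shown, and the table does not restrict the cumulative comparison.

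**End of Stage 1 is inferred.** The C-SSRS paragraph does not define it. Visit 18 for 125 mg is explicit elsewhere in the SAP. Visit 13 for the other groups follows from the passages set out above. Protocol 6.0 (the same dose on three occasions) and Protocol 6.2.12 (Stage 1-only subjects followed from a third session) read as if every group had three Stage 1 sessions. They conflict with Protocol 5.0 and 6.2.7, SAP 4.0 and footnote J, and must be reconciled. Nothing in them supplies a common cut-off.

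**The effect is small.** This stands. The expected excess is below one subject at risks up to 0.10, entry excludes serious suicide risk (Protocol 5.3.2), adverse events are the primary safety measure (SAP 8.9.4), and this is a 24-subject pilot. A reader might infer inflated false significance; at plausible low risks the error rate is below 0.05.

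**Stage 2.** A reader might infer a worse imbalance of up to five sessions (2 + 3) against three. That requires carrying full-dose subjects into a stage they do not have. The SAP names no population here, but its Crossover population and crossover analyses cover low and medium dose only. On that reading planned sessions are equal.

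**Conclusion.** The point holds conditionally. The plan leaves the contrast, population and cut-off of this comparison open. If the groups are compared on cumulative on-study frequencies, full dose is observed over three sessions and the others over two, and nothing in either document sets a common window. The resulting inflation of the full-dose percentage is a factor of about 1.2 to 1.5 over the assumed risks and correlations. It rests on equal risk per session at every dose and full attendance; the risks and correlations are assumptions, not document figures. The damage is to the reading of the displayed percentages in a stated safety comparison, not to type I error. Minor to moderate severity.

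**What to change.** In SAP 8.9.4:

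1. State the contrast, population and window of the cumulative C-SSRS comparison.
2. Restrict the between-dose comparison to first dose through visit 13 in every arm. Each arm then has two blinded sessions and 14 scheduled contacts, and equal risk gives equal expected percentages.
3. Define the time-period categories so that one boundary falls at visit 13.
4. Show the full-dose third session and Stage 2 separately, by dose received, as descriptive output.
5. State that the Stage 2 cumulative comparison covers crossover subjects only.
6. If the lifetime versus on-study contrast is meant within subjects, present it descriptively or with a paired exact test, since chi-squared and Fisher tests ignore the pairing.

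The cost is SAP wording and some extra table columns. C-SSRS is already scheduled at every visit needed, so no new data are required.

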### Subjective Units of Distress (SUD)

Descriptive statistics for SUD scores will be calculated by treatment group and time period with counts and percentages.

### Visual analog scale for Tinnitus and/or Pain visual analog scale

Formal analysis of Changes in Tinnitus and/or Pain visual analog scale scores will only occur if three or more subjects complete Changes in Tinnitus and/or Pain visual analog scale at baseline and primary endpoint. Likewise, formal between-groups analyses will not be performed if all primary endpoint scores are from subjects assigned to the same condition. T-tests will be performed on the difference between baseline and primary endpoint Changes in Tinnitus and/or Pain visual analog scale scores in the full dose and comparator dose conditions, with p set at 0.05. If the only scores available are for subjects in a single condition, then a paired t-test will be performed comparing baseline and primary endpoint Changes in Tinnitus and/or Pain visual analog scale scores, with p set at 0.05.

### Vital signs

Vital signs (heart rate, body temperature, systolic and diastolic blood pressure) will be summarized using descriptive statistics at baseline and at each post-baseline time point. For experimental sessions, mean peak heart rate, blood pressure, and body temperature will be analyzed by condition with ANOVA, with t-tests for pairwise comparisons. Occurrences of systolic and diastolic blood pressure, heart rate, and body temperature readings above the pre-determined cutoff will be displayed with numbers and percentages by timepoint. A within-subjects t-tests for pre- and post-drug endpoints will be conducted for each session for heart rate, blood pressure, and body temperature.

